#### 4.3.3 Demographic/Baseline Characteristic and Descriptive Endpoint(s)

- Change from baseline to 12, 18 and 24 months post-permanent implant for quality of life measured using the EQ5D questionnaire.
- Change from baseline to 3, 12, 18, and 24 months post-permanent implant for pain catastrophizing measured using the PCS.
- Change from baseline to 12, 18 and 24 months post-permanent implant for anxiety measured using the STAI.
- Change from baseline to 12, 18 and 24 months post-permanent implant for depression measured using the PHQ9.
- Change from baseline to 3, 12, 18 and 24 months post-permanent implant for fear avoidance measured using the TSK.
- Change from baseline to 12, 18 and 24 months post-permanent implant for sleep measured using the MOS Sleep Scale.
- Change from baseline to 12, 18 and 24 months post-permanent implant for physical function measured using the PROMIS Physical Function Scale.
- Change from baseline to End of Trial system evaluation 3, 12, 18, and 24 months post-permanent implant in pain assessed by using the NRS.
- Demographics and baseline characteristics.
- Patient waveform preference (if applicable).
- Patient satisfaction at End of Trial system evaluation 3, 6, 12, 18, and 24 months post-permanent implant.
- Global improvement of the patient by using the Patient Global Impression of Change (PGIC) at End of Trial System Evaluation 3, 6, 12, 18, and 24 months.
- Medication usage measured in decrease in chronic pain related medication intake since baseline at 3, 6, 12, 18, and 24 months post-permanent implant.
- Battery consumption and/or recharging activities.
- Stimulation Assessment measured by using the Stimulation Assessment Form at 3, 6, 12, 18, and 24 months post-permanent implant as well as any unscheduled visit where reprogramming occurs.
- Program information including amplitude, pulse width, frequency and electrode configuration.
- System information including device type, model number, serial number and number of leads.
- Proportion of device, or procedure-related Serious Adverse Events (SAE)'s and non-serious adverse events in subjects who receive permanent implant of the SCS system.

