- Medication usage measured in decrease in chronic pain related medication intake since baseline at 3, 6, 12, 18, and 24 months post-permanent implant by frequencies and percentages.
- Battery consumption and/or recharging activities at 3, 6, 12, 18, and 24 months will be summarized by frequencies and percentages.
- Stimulation Assessment measured by using the Stimulation Assessment Form at 3, 6, 12, 18, and 24 months post-permanent implant will examine types of perceived stimulation as well as stimulation coverage and intensity.
- Program information including amplitude, pulse width, frequency and electrode configuration will be summarized.
- System information including device type, model number, lot number, and number of leads will be summarized.
- Device, or procedure-related SAEs and non-serious AEs in subjects who receive permanent implant of the SCS stimulation system will be summarized by frequencies and percentages.

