## 6.3 Overall Sample Size

The study aims to enroll 267 subjects based on assumptions drawn from experience with the Prodigy I study. Assuming a trial failure rate of 30%, and an attrition rate of 10% between baseline and trial, and 14% from permanent implant to 6-month follow-up, 168 subjects are projected to complete the permanent implant and 145 subjects are projected to complete the 6-month follow-up for primary endpoint evaluation. One hundred forty-five (145) subjects with evaluable NRS data at baseline and 6-month visit provides a 95% confidence interval on the NRS change from baseline to 6-month with half interval width of 0.49 assuming the standard deviation of the NRS change is 3.

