## Clinical Investigation Plan

Safety surveillance and the safety reporting will continue until the last investigational visit has been performed, the subject is deceased, the subject/Investigator concludes his participation into the clinical investigation or the subject withdrawal from the clinical investigation.

All adverse event data including deaths will be collected throughout the clinical investigation and will be reported to the Sponsor on a CRF.

Adverse events will be monitored by the Investigator until they are adequately resolved or the subject has ended his/her participation in the trial, whichever comes first. The status of the subject's condition should be documented and reported to the Sponsor at each visit.

Per the CIP, the applicable reportable adverse event data including deaths will be collected throughout the clinical study and will be reported to the Sponsor through the EDC system. The Sponsor will ensure that all applicable events are reported to the relevant authorities as per regulations. The Investigator must notify the IRB/EC, if appropriate, in accordance with national and local laws and regulations, of the AEs reported to the Sponsor.

Reportable events to Sponsor are considered:

- All non-Serious Adverse Device Effects (procedure/device related)
- All Serious Adverse Events (whether or not the event is considered device or procedure related)
- Adverse events related to MRI scan

All the above events will be reported to the Sponsor, as soon as possible, but no later than 3 calendar days from the day the site personnel became aware of the event, or as per the investigative site's local requirements if that requirement is more stringent. The date the site staff became aware that the event met the criteria for an SAE must be recorded in the source documents.

For unexpected failure modes or unexpected adverse events, the site should follow their standard reporting practices for medical device reporting (MDR)/Vigilance reporting for medical devices per the regulations.

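### Adverse events are to be summarised only as crude frequencies and percentages, with no time window or allowance for unequal follow-up; adding a cumulative incidence table would be a cheap improvement

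*Combined protocol and SAP*

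**What the plan says.** Section 4.3.3 lists the safety endpoint as "Proportion of device, or procedure-related Serious Adverse Events (SAE)'s and non-serious adverse events in subjects who receive permanent implant of the SCS system". Section 6.1.3 gives the whole of its analysis: these events in subjects who receive "permanent implant of the SCS stimulation system will be summarized by frequencies and percentages". Most outcome bullets in that section name their visits. The adverse event bullet names none.

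Four other sections determine how long each subject is observed:
- Section 6.3 assumes attrition of "14% from permanent implant to 6-month follow-up", and "145 subjects are projected to complete the 6-month follow-up for primary endpoint evaluation". It says nothing about attrition after month 6.
- Section 8.2 states that "Safety surveillance and the safety reporting will continue until the last investigational visit has been performed", or until death, the end of participation or withdrawal.
- Section 5.3.11 withdraws subjects who are explanted and cannot be re-implanted.
- Section 6.4 times the final report for when every enrolled subject has completed month 24 or has discontinued earlier.

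Section 6.1.4 allows imputation where appropriate for dropouts and withdrawals. It names no method, and mentions neither adverse events nor time at risk.

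**The concern.** A percentage of all implanted subjects gives the same weight to someone observed for four months and someone observed for 24. A subject who leaves event-free early stays in the denominator but can no longer contribute an event. If the percentage is then read as the risk by 12 or 24 months, it will tend to be low, and more so the greater the dropout. Part of the study's rationale in Section 2 is that outcomes beyond 12 months had not been reported, so readers are likely to want a risk tied to a time point. The planned summary cannot give one.

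There is also an ambiguity of definition. A proportion of events in subjects could mean subjects with at least one event, or events divided by subjects. The two differ when a subject has repeat events.

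**Working it through.** **The plan's own figures.** Section 6.3 starts from 267 enrolled, with 10% attrition before the trial stage, 30% trial failure and 14% attrition from implant to month 6.
- Implanted: 267 × 0.90 × 0.70 = 168.2 (stated: 168).
- Month-6 completers: 168.2 × 0.86 = 144.7 (stated: 145).

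Both reproduce.

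**Assumptions not in the documents.** A 24-month event risk of 20%, a constant event hazard, and the rate of loss after month 6.
- Event hazard λ = −ln(0.80)/24 = 0.00930 per month.
- Loss hazard δ = −ln(0.86)/6 = 0.02514 per month.

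The expected crude proportion is the integral over 0 to 24 months of λ·exp(−λu)·R(u), where R(u) is the fraction still under surveillance.

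**Case A: all 14% is non-informative loss of adverse event follow-up, and none follows.**
- Months 0–6: λ/(λ+δ) × [1 − exp(−6(λ+δ))] = 0.2700 × 0.1867 = 0.0504.
- Months 6–24: exp(−6(λ+δ)) × [1 − exp(−18λ)] = 0.8133 × 0.1541 = 0.1253.
- Crude = 17.6% against 20%; understatement 1 − 0.1757/0.20 = 12.1%.

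**Case B: the same loss rate continues to month 24.**
- Retention is 0.86⁴ = 54.7%, about 92 of 168.
- Crude = 0.2700 × [1 − exp(−24(λ+δ))] = 0.2700 × 0.5624 = 15.2%; understatement 24.1%.

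Intermediate later losses of 3% and 7% per 6 months give 17.0% and 16.3%. At event risks of 10% and 30% the relative figures barely move: 12.2% and 12.0% in Case A, 24.5% and 23.6% in Case B.

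**Case C: half of the attrition is death or permanent explant.** These are competing events. The right comparator is then the cumulative incidence, computed with only that half (hazard δ/2) removing subjects from risk.
- No loss after month 6: crude 17.6% against 18.7%; understatement 6.2%.
- Same rate to month 24: crude 15.2% against 17.4%; understatement 12.5%.
- If all attrition is competing, the crude proportion equals the cumulative incidence and the understatement is 0%.

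**Case D: only half of the 14% stops surveillance** (7% lost by month 6).
- No loss after month 6: crude 18.8% against 20%; understatement about 6%.
- 7% per 6 months throughout: crude 17.5%; understatement about 13%.

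**Case E: events cluster early.** For events spread evenly over the first w months, the understatement is 1 − [1 − exp(−δw)]/(δw).
- w = 1: 1.2%.
- w = 3: 3.7%.

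**The case against.** The strongest reply is that the plan never claims a 24-month risk. No text says that an early leaver counts as event-free to month 24, and a crude percentage correctly describes what was observed. Safety is one of many descriptive endpoints, the devices are market released, and Section 6.6 sets no statistical stopping criteria. This stands, and it keeps the point at the level of an improvement.

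Three further objections limit the size, and all stand:
- Section 5.9 lists death as a reason for withdrawal and Section 5.3.11 adds explant. That share of attrition does not bias a cumulative incidence in which death and explant are competing events.
- The 14% is attrition up to the 6-month primary evaluation. Section 5.9 separates a missed visit from loss to follow-up, and Section 8.2 ends surveillance at withdrawal, not at a missed visit.
- Several risks in Section 7.1.1, such as hematoma, infection, CSF leakage and seroma, may occur soon after surgery. Lead migration, lead failure and battery depletion fit the evenly spread assumption better.

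Two stronger inferences fail. A reader might say that the result would distort comparison with other studies, but Section 6.1.1 plans external comparison only for efficacy. A reader might also say that safety is singled out for lack of confidence intervals, but none of the categorical endpoints in Section 6.1.3 has one.

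Section 6.1.4 does not answer the concern, because unspecified imputation is not an allowance for time at risk.

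**Conclusion.** The omission is real. The safety summary has no time window or exposure basis, its counting unit is unclear, and follow-up will be unequal on the plan's own figures. A crude percentage read as 12- or 24-month risk will tend to be too low.

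A reader might infer that cumulative risk is understated by an eighth to a quarter. The documents do not support that as a general range. About 12% needs evenly spread events and the full 14% as non-informative loss of surveillance. About 24% needs the same loss rate to continue to month 24, which the plan does not state. The understatement is about 6% to 13% if half the attrition is competing or only half of the 14% ends surveillance; the top of that range also assumes continued later loss. It is near zero to about 4% if events fall in the first three months or attrition is mostly death or explant. All figures are relative, and the cases with evenly spread events use an assumed 20% risk and constant hazard. No planned decision depends on the result, so this is a cheap improvement.

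**What to change.** In Sections 4.3.3 and 6.1.3:
- Define the endpoint as subjects with at least one device- or procedure-related event, with serious and non-serious events shown separately and event counts beside them.
- Add cumulative incidence at 6, 12 and 24 months from permanent implant, with 95% confidence intervals and numbers at risk. Censor at withdrawal, and treat death and permanent explant as competing events.
- Report repeat events per 100 patient-years.
- Keep the crude counts and percentages.

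The cost is revised wording and one extra table. It needs event onset dates, which are assumed to be on the adverse event CRF (the CRFs are held separately), together with implant and withdrawal dates. No visit or sample size changes. The reported risk may look slightly less favourable. Censoring at withdrawal still assumes that those who leave have the same later risk as those who stay, so reasons for withdrawal should be tabulated alongside.

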#### **6.1.4 Missing Data**

Imputation methods will be used as appropriate to account for missing data, subject dropouts and withdrawals. If spurious data are discovered, these data will be excluded from analyses. Specific methods for handling missing data and reasons for exclusion of any data from analyses will be summarized where appropriate.

#### **6.1.1 Subgroup Analysis**

Primary and secondary endpoints will be stratified by the subjects who had an 'on-the-table trial' and subjects who had a BurstDR trial.

## 6.2 Justification of Clinical Investigation Design

The study is designed as a post-market, international, multicenter, interventional, prospective, single-arm study. The investigation will be conducted in approximately 30 centers in EMEA, US, Canada, and ANZ. The international and long-term follow-up study design will provide the real-world experience of multiple waveform enabled neurostimulator in patients with chronic, intractable pain of the trunk and/or limbs.

## 6.3 Overall Sample Size

The study aims to enroll 267 subjects based on assumptions drawn from experience with the Prodigy I study. Assuming a trial failure rate of 30%, and an attrition rate of 10% between baseline and trial, and 14% from permanent implant to 6-month follow-up, 168 subjects are projected to complete the permanent implant and 145 subjects are projected to complete the 6-month follow-up for primary endpoint evaluation. One hundred forty-five (145) subjects with evaluable NRS data at baseline and 6-month visit provides a 95% confidence interval on the NRS change from baseline to 6-month with half interval width of 0.49 assuming the standard deviation of the NRS change is 3.

## 6.4 Timing of Analysis

The analysis of primary and secondary endpoints will be conducted when 145 subjects have a permanent system implant and complete the 6-month follow-up endpoint evaluation. The final report will be conducted after all enrolled subjects either complete the 24-month visit or are discontinued from the study prior to the 24-month visit.

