## **4 Clinical Investigation Design**

### **4.1 Clinical Investigation Design**

The study is designed as a post-market, international, multicenter, interventional, prospective, single-arm study. The purpose of this clinical study is to examine pain relief and other outcomes for subjects with chronic, intractable pain of the trunk and/or limbs who use BurstDR stimulation during the trial evaluation period and at 6, 12, 18 and 24 months after permanent system implant. Furthermore, the study seeks to explore sustainable pain relief, psychological outcomes, and stimulation usage patterns with a device capable of delivering multiple stimulation modes (BurstDR and tonic) through 24 months post-permanent implant. Finally, this study will collect MRI safety information, when available, for enrolled patients.

The investigation will be conducted in approximately 30 centers in EMEA, US, Canada and ANZ. Estimated enrollment duration is approximately 18 months with 24 months follow-up. Approximately 267 subjects will be enrolled in the study. A maximum of 53 subjects can be included per center. The study may continue up to 4 years, dependent on the rate of enrollment (approximately 18 months enrollment + 24 months follow-up + time to close the investigation and provide final report).

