### **6.1.3 Demographic/Baseline Characteristic and Descriptive Endpoints**

The following descriptive endpoints will be reported:

- Change from baseline to 12, 18, and 24 months post-permanent implant for quality of life measured using the EQ5D questionnaire will be summarized by mean, standard deviation and 95% confidence interval.
- Change of the PCS score from baseline at 3, 12, 18 and 24 months post-permanent implant will be summarized by mean, standard deviation, and 95% confidence interval.

- Change from baseline to 12, 18 and 24 months post-permanent implant for anxiety measured using the STAI will be summarized by mean, standard deviation, and 95% confidence interval.
- Change from baseline to 12, 18 and 24 months post-permanent implant for depression measured using the PHQ9 will be summarized by mean, standard deviation, and 95% confidence interval.
- Change from baseline to 3, 12, 18 and 24 months post-permanent implant for fear avoidance measured using the TSK will be summarized by mean, standard deviation, and 95% confidence interval.
- Change from baseline to 12, 18 and 24 months post-permanent implant for sleep measured using the MOS Sleep Scale will be summarized by mean, standard deviation, and 95% confidence interval.
- Change from baseline to 12, 18 and 24 months post-permanent implant for physical function measured using the PROMIS Physical Function Scale will be summarized by mean, standard deviation, and 95% confidence interval.
- Change from baseline to End of Trial System Evaluation 3, 12, 18, and 24 months post-permanent implant for pain measured using the NRS will be summarized by mean, standard deviation, and 95% confidence interval.
- Demographics and medical history will be reported. The continuous variable(s) will be summarized by mean and standard deviation. The categorical variable(s) will be summarized by frequencies and percentages.
- Patient waveform preference at 3, 6, 12, 18, and 24 months post-permanent implant will be summarized by frequencies and percentages for participants who had multiple waveforms available to choose from.
- Patient satisfaction at End of Trial System Evaluation 3, 6, 12, 18, and 24 months post-permanent implant will be summarized by frequencies and percentages.
- Global improvement of the patient by using the Patient Global Impression of Change at End of Trial System Evaluation 3, 6, 12, 18, and 24 months will be summarized by frequencies and percentages.

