## 6.5 Interim Analysis

An interim analysis of descriptive endpoints will be performed when all enrolled subjects either reach the 12-month visit or are discontinued from the study prior to the 12-month visit.

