## **15 Reporting Results on ClinicalTrials.gov Website**

The clinical investigation will be registered on ClinicalTrials.gov. A full report of the pre-specified outcomes, regardless of the results, will be made public through the ClinicalTrials.gov website no later than 12 months after clinical investigation completion, as required by section 801 of the Food and Drug Administration (FDA) Amendments Act.

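### Does starting the 6-month analysis at 145 completers, with no alternative start point, leave the primary result without a date?

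*Combined protocol and SAP*

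**What the plan says.** Section 6.4 (Timing of Analysis) ties the primary and secondary analysis to a count: it "will be conducted when 145 subjects have a permanent system implant and complete the 6-month follow-up endpoint evaluation".

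Section 6.3 (Overall Sample Size) gives the same number as a projection: "145 subjects are projected to complete the 6-month follow-up for primary endpoint evaluation". Enrolment is worded as a target in two places: "The study aims to enroll 267 subjects based on assumptions drawn from experience with the Prodigy I study" (section 6.3) and "Approximately 267 subjects will be enrolled in the study" (section 4.1).

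The other two analysis points are tied to everyone's status, not to a count. For the final report, section 6.4 says: "The final report will be conducted after all enrolled subjects either complete the 24-month visit or are discontinued from the study" before that visit. For the 12-month look, section 6.5 says: "An interim analysis of descriptive endpoints will be performed when all enrolled subjects either reach the 12-month visit or are discontinued" before that visit.

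The 12-month look is confined to descriptive endpoints. For pain, section 6.1.3 lists these as "Change from baseline to End of Trial System Evaluation 3, 12, 18, and 24 months post-permanent implant for pain measured using the NRS". The 6-month value is absent because it is the primary endpoint (section 4.3.1).

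**The concern.** An expected value is being used as a trigger. If enrolment stops at 267 and the planning rates hold, the count reaches 145 only about half the time, and section 6.4 does not say what happens otherwise. The other two analysis points cannot fail in this way, because discontinued subjects count towards them.

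Read literally, a shortfall gives an odd order of reporting. Pain change at 3 and 12 months would be summarised at the 12-month look, while the 6-month primary endpoint would have no scheduled analysis before the final report. The gap between a subject's 6-month and 24-month visits is 24 − 6 = 18 months. The sponsor would then choose the read-out date in an open, single-arm study whose data it analyses itself (section 9). If that choice could move the estimate or hide a result, the plan would need to fix the date.

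**Working it through.** **Inputs (all from section 6.3).** Enrolment 267; attrition from baseline to trial 10%; trial failure 30%; attrition from implant to 6 months 14%; standard deviation of the NRS change 3.

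**1. The plan's own figures.**
- Implants: 267 × 0.90 × 0.70 = 168.2 (stated 168).
- Completers: 168.2 × 0.86 = 144.7 (stated 145).
- Half-width: 1.96 × 3/√145 = 0.488 (stated 0.49).

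All three reproduce.

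**2. Chance of a shortfall.** The probability that an enrolled subject completes 6 months is p = 0.90 × 0.70 × 0.86 = 0.5418. Treat the number of completers X as Binomial(267, p), with independent subjects.
- Mean: 144.66.
- Standard deviation: √(267 × 0.5418 × 0.4582) = 8.14.
- 95% range: 129 to 161.
- P(X < 145) = 0.49.

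A value near one half is what any threshold set at its own expected value gives, so it says little about this study. It moves readily with the inputs. In the table one rate is changed at a time; the alternative rates are my assumptions.

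| Trial failure | Attrition to 6 months | Expected completers | P(X < 145) |
|---|---|---|---|
| 30% | 14% | 144.7 | 0.49 |
| 25% | 14% | 155.0 | 0.10 |
| 35% | 14% | 134.3 | 0.89 |
| 30% | 10% | 151.4 | 0.20 |
| 30% | 18% | 137.9 | 0.79 |

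At the planning rates, enrolling 280 instead of 267 lowers P(X < 145) to 0.19. A shortfall is therefore possible and not remote, but its probability cannot be pinned down.

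**3. What a shortfall does to precision.** Half-width = 1.96 × 3/√n.

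| Completers n | Half-width (NRS points) |
|---|---|
| 145 | 0.49 |
| 138 (mean count when short, planning rates) | 0.50 |
| 129 (lower end of 95% range, planning rates) | 0.52 |
| 118 (lower end of 95% range, 35% trial failure) | 0.54 |

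Even the last row is only 0.54 − 0.49 = 0.05 points wider than planned, on a 0 to 10 scale.

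**4. What a shortfall does to the estimate.** Section 6.1.1 (Primary Endpoint) takes all subjects with NRS at baseline and at 6 months. It does not mention 145. The output is a mean, standard deviation, median, range and 95% interval, compared descriptively with other trials. There is no test, no alpha to spend and, under section 6.6, no statistical stopping rule. Once enrolment has closed and every implanted subject has completed or left before 6 months, the set of completers is fixed, and waiting until the final report adds none.

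**5. What ensures that the result is reported.** Section 15 commits to this: "A full report of the pre-specified outcomes, regardless of the results, will be made public through the ClinicalTrials.gov website". Section 6.7 requires any deviation from the statistical plan to be documented in the report that carries the results. A 6-month analysis run on fewer than 145 completers would be such a deviation.

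**The case for a change.** The strongest argument for a change is that the plan shows its own remedy. The final report and the 12-month look both allow for discontinued subjects; only the trigger for the primary endpoint does not. One clause would close the gap at almost no cost, and a date fixed in advance is better than one chosen by a sponsor who can see the data. Nor does section 6.7 supply a date: it records a departure but does not prevent one.

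All of that stands as a point of drafting. It does not show harm to the result. The choice left open is when to summarise a set of completers that the protocol already defines, with no test whose error rate could be inflated. A read-out while subjects were still due would be visible in the report, and nothing suggests that the final report would leave out later completers, although section 6.4 does not list its contents.

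There is also a natural reading on which little is missing: 145 is the precision target, 267 is the estimate of what it takes, and enrolment, stated only as an aim, is adjusted to reach it. The plan does not state that rule, so this reading cannot be relied on, but it fits the wording.

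A further suggestion, to label 145 in section 6.3 as an expected yield with a range of 129 to 161, gains nothing. Section 6.3 already calls the number a projection, and the range is too narrow once the rates are uncertain: with trial failure between 25% and 35% (assumed), the 95% limits run from 118 to 171. Repeating the 6-month analysis in the final report would deal with more than 145 completers, which is a different matter from a shortfall.

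**Conclusion.** The observation is accurate: section 6.4 sets the start of the primary analysis at an expected count and gives no alternative. No change to the plan is needed, because the gap concerns only the date of the 6-month read-out. The population, the estimate and its interpretation do not depend on reaching 145. The loss of precision is about 0.03 NRS points in half-width at 129 completers (0.52 against 0.49) and 0.05 at 118. Analysts would fill the gap sensibly by analysing all completers once no more can arrive, and section 6.7 would put that on record.

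This rests on four assumptions: the planned standard deviation of 3; independent subjects at the stated rates, for the probabilities; the primary analysis remaining descriptive, as section 6.1.1 has it; and the final report carrying the 6-month result, which is a reasonable inference from sections 6.4 and 15 but is not stated outright. If a hypothesis test or a decision rule were attached to the 6-month result, the start point would matter more.
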